4.7.2 Dose Escalations

Part A will utilize an accelerated dose escalation design to enroll one patient to dose levels 1, which will be converted to a traditional 3+3 design when a grade 2 or higher toxicity occurs during cycle 1 therapy at these dose levels unless it is clearly related to disease progression or extraneous cause, whichever comes first. Intra-individual dose escalation will be allowed in this part A study when it is approved by sponsor and investigator.

Upon completion of the DLT evaluation in patients in the high-dose level cohorts and confirmation that the dose is safe, patients in the low-dose level cohorts may be adjusted to the high-dose level study treatment that has completed the evaluation, with the consent of the principal investigator and the sponsor.

Subjects in the dose expansion study may be allowed to transfer to a higher dose level if the benefits outweigh the risks, as assessed by the investigator, and determined by the SMC. The higher dose level should be safe and confirmed by the phase Ia dose escalation study, as assessed by the investigator and determined by the SMC.

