	
of $>38.3^{\circ}\text{C}$ (101°F) or a sustained temperature of $\geq 38^{\circ}\text{C}$ (100°F) for more than one hour;
 
• CTCAE Grade 3 thrombocytopenia ($\geq 25,000/\text{mm}^3$ and $<50,000/\text{mm}^3$) associated with bleeding; 
2. Non-hematological toxicity:
 
• Hy's law, defined as:
◇ AST or ALT > 3 x the upper limit of normal (ULN) AND◇ Total bilirubin > 2 x ULN AND◇ Alkaline phosphatase < 2 x ULN AND◇ No other reason for liver injury• ALT or AST >8x ULN, ALT or AST >5x ULN for more than 2 weeks, ALT or AST >3x ULN and (TBL >2x ULN or INR >1.5)
◇ For patients with hepatic metastases, AST or ALT > 8 x ULN or ALT or AST > 5 x ULN for ≥ 14 days• Grade > 3 non-hematologic toxicity with the exception of the following
◇ Grade 3+ fatigue ≥ 7 days regardless of baseline grade;◇ Grade 3 nausea and vomiting, lasting ≤ 2 days with optimal medical management;◇ Grade 3 diarrhea lasting ≤ 3 days with optimal medical management◇ $\geq 3+$ non-hematologic abnormalities should also include laboratory values that cause symptoms. 
MTD Evaluation period:
 
• Part A: FWD1802 single dose run-in period (C0:D1-D6 intake on D1, then off until D6) and 1st 28-day treatment cycle (C1:D1-D28), total of 34 days;• Part B: the 1st treatment cycle of FWD1802 in combination with palbociclib (C1:D1-D28)
--	---

Duration of treatment	Reiterated treatment cycles of 4 weeks until progression disease based on radiological evaluation, undue drug toxicity, withdrawal of consent or death, whichever occurs first.
PK/PD Sample	Please see Section 7.5.1 PK Samples and Section 7.3.7 18F-FES PET/CT.

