4.2 Methodology

4.2.1 Part A – Dose Escalation of FWD1802 as a Monotherapy

Part A study will be conducted in subjects diagnosed with ER+/HER2- unresectable locally advanced or metastatic breast cancer, to evaluate the safety and tolerability, PK, PD and preliminary anti-tumor activity of FWD1802 Tablet, and to determine RDEs. A maximum of 27 subjects will be enrolled. They will be sequentially allocated to 5 planned dose cohorts: 25 mg, 75 mg, 150 mg, 300 mg and 450 mg.

Subjects enrolled will be orally administered a single dose of FWD1802 Tablet on Cycle 0 Day 1 (C0D1), followed by a 5-day observation period to evaluate the PK and safety of the drug product. Starting on Cycle 1 Day 1 (C1D1), FWD1802 Tablet will be orally administered continuously once or quaque die (QD) for 28 consecutive days of each cycle. The DLT observation period is set as 34 days after the initial administration (1 cycle) (single-dose period and the first 28-day cycle). The second cycle and subsequent cycles will last for 28 days per cycle. The patients will continue to receive the study treatment until disease progression, death, unacceptable toxicity, withdrawal of informed consent, or other reasons to discontinue study treatment occurs, whichever comes first.

Part A will utilize an accelerated dose escalation design to enroll one patient to dose levels 1, which will be converted to a traditional ‘3+3’ design when a grade 2 or higher toxicity occurs during cycle 1 therapy at these dose levels unless it is clearly related to disease progression or extraneous cause, whichever comes first.

Before starting the next dose level, all subjects (n=1, 3, or 6) at the current dose level must complete the DLT observation period. The Safety Monitoring Committee (SMC) will decide whether the study will proceed to the next dose level. Please refer to Section 4.7 Dose modifications.

Based on the safety data, a higher dose level beyond dose level 5 or an intermediate dose level can be explored as determined by the SMC.

The planned escalation dose levels are shown below:

Table 8. The Planned Dose Escalation Levels of FWD1802 in Phase Ia Study

Groups	Dose (mg) *	Percentage of escalation (%)	Number of subjects
1(Starting dose)	25	/	1~3
2**	75	200%	3~6
3**	150	100%	3~6
4**	300	100%	3~6
5**	450	50%	3~6

**Dose levels will be determined based on the results of lower doses, at the discretion of SMC.

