4.4 Dose Escalation/Stopping Criteria

The combination of ‘accelerated escalation’ and the traditional ‘3+3’ was used for Part A study. It’s planned that one eligible subject will be enrolled for the evaluation of the first

dose levels (25 mg) using intra-individual dose escalation, when it is approved by sponsor and investigator. If no \geq grade 2 adverse event (defined as any \geq grade 2 adverse event occurs during the DLT observation period unless it is clearly related to disease progression or extraneous cause) occurs during the DLT observation period, dose escalation enters the 2nd dose group with the traditional '3+3' mode. Otherwise, additional 2 subjects will be added to the current dose group, and the dose group and subsequent dose groups will switch to a '3+3' dose escalation design. Before starting the next dose level, all subjects (n=1, 3, or 6) at the current dose level must complete the DLT observation period and be determined by the Safety Monitoring Committee (SMC) to proceed to the next dose level. If no DLT has occurred at the end of the DLT observation period, subjects may adjust its dose level to any higher dose level that no DLT events have occurred during the DLT observation period, as assessed by the investigator and determined by the SMC, and on the condition that the investigator considers safe for the subjects.

If MTD cannot be determined at this part due to too few DLT events, a higher dose or an intermediate dose can be explored as needed, after the dose escalation reaches the highest predicted dose or is determined by the SMC.

The traditional '3+3' increment rule for dose escalation is as follows:

- The dose will be escalated if no DLT has been reported in the first 3 subjects of this dose group after DLT observation period.
- If 1 of the first 3 subjects enrolled has DLT occurred, then 3 additional subjects will be enrolled, with totally 6 subjects in this dose group.

-If only 1 DLT event occurs in these 6 subjects, then the dose will be escalated.

-If ≥ 2 DLT events occur in these 6 subjects, then no more subjects will be enrolled in this dose group and the dose escalation will be stopped. The SMC will decide whether to use the intermediate dose as the next dose level for the study or to terminate the dose escalation.

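### The trigger for converting the one-patient 25 mg level to 3+3 covers Cycle 1 only in Sections 4.2.1 and 4.7.2, but the whole DLT period, including the Cycle 0 run-in, in Section 4.4

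*Protocol*

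**What the plan says.** The protocol states the conversion trigger for the 25 mg level in three places.

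- **Sections 4.2.1 and 4.7.2** use the same words: the level converts to 3+3 "when a grade 2 or higher toxicity occurs during cycle 1 therapy at these dose levels".
- **Section 4.4** counts any event meeting "grade 2 adverse event occurs during the DLT observation period unless it is clearly related" to progression or another outside cause. If there is none, "dose escalation enters the 2nd dose group with the traditional" 3+3 scheme. Otherwise "additional 2 subjects will be added to the current dose group, and the dose group and subsequent dose groups will switch" to 3+3.

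The labels that decide what Cycle 1 means are in Section 4.2.1 and the synopsis.

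- Section 4.2.1 has patients "orally administered a single dose of FWD1802 Tablet on Cycle 0 Day 1 (C0D1), followed by a 5-day observation period". Then: "Starting on Cycle 1 Day 1 (C1D1), FWD1802 Tablet will be orally administered continuously".
- The synopsis gives the Part A evaluation period as "FWD1802 single dose run-in period (C0:D1-D6 intake on D1, then off until D6) and 1st 28-day treatment cycle", 34 days in total.
- Section 4.2.1 gives the same total with a looser gloss: "The DLT observation period is set as 34 days after the initial administration (1 cycle) (single-dose period and the first 28-day cycle".

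**The concern.** In the protocol's own labels the first dose belongs to Cycle 0, and Cycle 1 begins only after the run-in. A trigger limited to Cycle 1 therefore does not reach an event that starts and ends in the run-in, whereas a trigger based on the DLT period does. The reader gets a different answer depending on the section consulted.

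The trigger decides whether one patient or three are observed at 25 mg before the 200% step to 75 mg (Table 8). This is a first-in-human study, and the days left out are those directly after the first human dose.

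**Working it through.** **1. Reproduce the stated DLT period.** The run-in is one dosing day plus five observation days (4.2.1), that is C0 D1–D6 in the synopsis: 1 + 5 = 6 days. Cycle 1 is 28 days. 6 + 28 = 34 days, which agrees with the stated figure.

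**2. Compare the trigger windows.**

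| Section | Window as worded | Days | Doses |
|---|---|---|---|
| 4.2.1, 4.7.2 | Cycle 1 | 28 | 28 |
| 4.4 | DLT observation period (C0 + C1) | 34 | 1 + 28 = 29 |
| Difference | Cycle 0 | 6 (6/34 = 17.6%) | 1 (1/29 = 3.4%) |

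Tables 1 and 11 show Cycle 0 as 4 days. On that count the difference is 4 of 32 days (12.5%).

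**3. Follow one case through.** Take a grade 2 event, not a DLT, that begins on C0D2 and resolves before C1D1. Under 4.4 two more patients are enrolled at 25 mg (1 becomes 3) and the level follows 3+3. The wording of 4.2.1 and 4.7.2 does not call for this, although it does not say that the event must be ignored.

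**4. How often would the wordings disagree?** The protocol gives no event rate, so this is illustrative. Let p be the probability of a sub-DLT grade 2 or higher event over the whole period, and s the share of cumulative risk that falls in Cycle 0. Then

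P(event in Cycle 0, none in Cycle 1) = (1 − p)^(1 − s) − (1 − p).

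| Risk model | s | p = 0.1 | p = 0.3 | p = 0.5 |
|---|---|---|---|---|
| Risk follows doses given | 1/29 = 0.0345 | 0.33% | 0.87% | 1.21% |
| Constant per day, 34 days | 6/34 = 0.1765 | 1.69% | 4.55% | 6.51% |
| Constant per day, 32 days | 4/32 = 0.125 | 1.19% | 3.19% | 4.53% |

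For example, with p = 0.3 and s = 6/34: 0.7^(28/34) − 0.7 = 0.7455 − 0.7000 = 0.0455.

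**The case against.** The best defence is that Section 4.4 already settles the matter. It is the dedicated escalation section and the only one that states both branches, so a run-in event falls under its second branch and two patients are added. Sections 4.2.1 and 4.7.2 say when the level converts, not that it converts only then, so a site that follows 4.4 breaches neither. The one-cycle gloss on the 34 days in 4.2.1 also suggests that Cycle 1 was loose shorthand for the whole period.

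Much of this stands, and it is why the effect is small. It does not remove the inconsistency:

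- The protocol states no order of precedence. After describing the SMC's decision on the next level, 4.2.1 sends the reader to Section 4.7, where the narrower wording is repeated, and not to 4.4.
- The gloss does not appear in 4.7.2. In 4.2.1 it sits beside separate C0D1 and C1D1 labels and beside a parenthesis that separates the single-dose period from the first 28-day cycle. It makes the term ambiguous and does not redefine it.

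The probabilities can fairly be called generous. Constant risk per day gives a drug-free run-in day the same weight as a day of continuous dosing. An event that persists into C1D1 might also be counted under the narrower wording. The lower, per-dose figures may therefore be nearer the truth, but the mismatch in wording does not depend on them.

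**Conclusion.** The inconsistency is real. As worded, 4.2.1 and 4.7.2 use a 28-day trigger window where 4.4 uses 34 days, and the 6 days left out contain the first human dose. This rests only on the protocol's own cycle labels.

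The practical effect is small. One patient at one dose level is concerned, DLTs count over the full period, the patient must complete that period, the SMC must approve the step, and 75 mg is run as 3+3 in any case. The chance that the wordings would lead to different actions is about 0.3% to 6.5%. That range depends on the assumed p of 0.1 to 0.5 and on the assumed risk models, none of which the protocol supplies. The wording should still be corrected, because it is a safety rule for a first-in-human escalation and the correction is almost free.

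**What to change.** In Sections 4.2.1 and 4.7.2, replace the reference to Cycle 1 therapy with: during the DLT observation period (including the Cycle 0 single-dose run-in), as specified in Section 4.4. All three sections then share the 34-day window.

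The cost is two sentences of protocol text. If the narrower wording would otherwise have been followed, there is also a slightly higher chance of adding two patients at 25 mg. The level could reach six in all if the 3+3 rule in 4.4 then expands it, whereas Table 8 plans one to three. If sites would have followed 4.4 anyway, the edit changes no decision and adds no patients.

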4.7.3 Temporary Withdrawal

Study treatment may be suspended (not more than 28 days) for any of the following treatment-related adverse events: Grade 2 or higher adverse events, if clinically indicated, study treatment should be suspended until the event returns to grade 1 or baseline levels (see Table 9)

The study drug may be discontinued for no more than 28 days until toxicity is relieved, or based on the investigator's judgment. If > 28 days, the patient continues to benefit from the treatment as assessed by the investigator, the patient may continue to receive the study treatment.

5 Study Population

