4.5 Definition of MTD

- The maximum tolerable dose (MTD) is defined as the highest dose level while the incidence of DLT is less than 33% in the dose escalation study during the DLT evaluation period.
- Six patients are required to establish the MTD. If only 3 patients have been evaluated in the previous dose level below the non-tolerated dose, the cohort should be expanded to 6 patients at the previous dose level below the non-tolerated dose. If DLT is not observed in the additional 3 patients, or 6 patients have been evaluated at the previous

dose level, the MTD will be confirmed at the previous dose level below the non-tolerated dose.

- If MTD is not established at the end of escalation, the maximum safety dose will be defined as the maximum administrated dose (MAD).
- The recommended dose for expansion(s) will be confirmed comprehensively based on the results of safety, tolerability, PK and PD. The RP2D should be a pharmacologically active dose and the dose should be selected by pooling and evaluating all available PK, PD, target engagement, efficacy, safety, and tolerability data to select the appropriate dose. There will need to be at least 6 patients at the recommended dose for expansion level(s) to evaluate the safety, PK, PD and tolerability. If the DLT does not occur during the DLT assessment period, the current highest dose level will not be considered as the basis of dose escalation and may be used as a reference to dose design and safety evaluation of the recommend dose.

Based on the safety data, a higher dose level beyond dose level 9 or an intermediate dose level can be explored as determined by the SMC.

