4.6 Definitions of Dose-Limiting Toxicity (DLT)

All AEs of the specified grades should count as DLTs except those that are clearly and incontrovertibly due to disease progression or extraneous causes.

1. Hematological toxicity:

- CTCAE Grade ≥ 4 thrombocytopenia;
- CTCAE Grade 4 neutropenia lasting >7 days;
- CTCAE Grade ≥ 3 febrile neutropenia, where Grade 3 febrile neutropenia is defined as ANC $<1000/\text{mm}^3$ and a single temperature of $>38.3^\circ \text{C}$ (101°F) or a sustained temperature of $\geq 38^\circ \text{C}$ (100°F) for more than one hour;
- CTCAE Grade 3 thrombocytopenia ($\geq 25,000/\text{mm}^3$ and $<50,000/\text{mm}^3$) associated with bleeding;
- CTCAE Grade 4 ($<25,000/\text{m}^3$) thrombocytopenia lasting >5 days;

2. Non-hematological toxicity:

- Hy's law, defined as:
 - ✧ AST or ALT > 3 x the upper limit of normal (ULN) AND
 - ✧ Total bilirubin > 2 x ULN AND
 - ✧ Alkaline phosphatase < 2 x ULN AND

- ◇ No other reason for liver injury
- ALT or AST >8x ULN, ALT or AST >5x ULN for more than 2 weeks, ALT or AST >3x ULN and (TBL >2x ULN or INR >1.5)
 - ◇ For patients with hepatic metastases, AST or ALT > 8 x ULN or AST or ALT > 5 x ULN for \geq 14 days
- Grade > 3 non-hematologic toxicity with the exception of the following
 - ◇ Grade 3+ fatigue \geq 7 days regardless of baseline Grade;
 - ◇ Grade 3 nausea and vomiting, lasting \leq 2 days with optimal medical management;
 - ◇ Grade 3 diarrhea lasting \leq 3 days with optimal medical management
 - ◇ \geq 3+ non-hematologic abnormalities should also include laboratory values that cause symptoms.

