4.7 Dose modifications

4.7.1 Dose Reductions

Dose reductions will be only allowed beyond DLT evaluation period in the dose escalation and expansion studies. Subjects who experience the unacceptable adverse events may continue treatment at the next lower dose level until disease progression or unacceptable toxicity. Adverse events considered for dose reduction should not include the events assessed by the investigator as exclusively related to underlying disease or other medical condition or concomitant treatment. The dose reduction guideline for general adverse events are outlined in Table 9. Provisions are not made for dose levels below 25 mg. If 25 mg once daily is determined to be unsuitable based on DLT as defined above, FWD1802 will be permanently discontinued.

Table 9 Dose reductions guideline for general adverse events

CTCAE grade	Follow-up procedures and dose reductions
CTCAE grade 1	Continue to receive study treatment at same dose level Monitor closely. Provide supportive therapy.
CTCAE grade 2	Discontinue study treatment if there are clinical symptoms. Monitor closely. Provide supportive therapy. Restart study treatment at the same dose level if resolved to CTCAE grade 1 or baseline within 14 days.
CTCAE grade 3	Discontinue study treatment if there are clinical symptoms. Monitor closely.

CTCAE grade	Follow-up procedures and dose reductions
CTCAE grade 4	Provide supportive therapy. Restart to study treatment at one dose level lower (except dose group 1) if resolved to CTCAE grade 1 or baseline. Discontinue treatment if CTCAE grade 3 AE occurs again. Restart to study treatment at one dose level lower if resolved to CTCAE grade 1 or baseline within 21 days. Discontinue study treatment if there are clinical symptoms. Monitor closely. Provide supportive therapy. Restart to study treatment at one dose level lower (except dose group 1) if resolved to CTCAE grade 1 or baseline within 21 days. If CTCAE grade 4 AE occurs again, discontinue permanently based on investigator and sponsor's judgement.

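### The 3+3 rule counts a patient as DLT-free if she reaches the end of a calendar window, even if a permitted toxicity hold left her with a quarter to half of her planned doses

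*Protocol*

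**What the plan says.** Protocol 4.4 gives the escalation rule: "The dose will be escalated if no DLT has been reported in the first 3 subjects of this dose group after DLT observation period". Its condition for opening the next level is that "all subjects (n=1, 3, or 6) at the current dose level must complete the DLT observation period", followed by an SMC decision. Section 4.5 adds: "Six patients are required to establish the MTD".

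The observation period is a number of days, not of doses. In Part A it is the single-dose run-in plus the first 28-day cycle, 34 days in all (4.2.1 and the Synopsis). In Part B it is the first 28-day cycle (Synopsis).

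On interruptions, 4.7.3 reads: "Study treatment may be suspended (not more than 28 days) for any of the following treatment-related adverse events: Grade 2 or higher adverse events". It refers to Table 9 and also lets a hold run past 28 days if the investigator sees continuing benefit. Section 4.7.1 restricts reductions: "Dose reductions will be only allowed beyond DLT evaluation period in the dose escalation and expansion studies". Section 4.7.3 has no matching restriction for holds. Table 9 allows a same-dose restart after a grade 2 event that resolves within 14 days. For grade 4 it says: "Restart to study treatment at one dose level lower (except dose group 1) if resolved to CTCAE grade 1 or baseline within 21 days".

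The DLT list in 4.6 has no item for a dose delay or missed doses. Sections 4.4 to 4.7 contain no minimum exposure, DLT-evaluable definition or replacement rule, and 10.2 has no DLT analysis set.

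**The concern.** A 3+3 rule assumes that each patient counted as a non-DLT was exposed to the cohort dose for the assessment period. Here a patient can develop a treatment-related toxicity below the DLT threshold, be taken off drug, and sit out the rest of the window. Section 5.4.2 asks sites to keep following a patient who stops temporarily, so she will normally reach the end of it. On the text of 4.4 she then adds one to the denominator and nothing to the DLT count.

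The error has one direction. Unexposed patients can only lower the observed DLT count, so the rule leans towards escalating past a toxic dose. A patient held for related toxicity is also plausibly among those more likely to have had a DLT with continued dosing. This is a first-in-human study with three or six patients per level: one DLT in six escalates, two in six stops. One patient can decide the outcome.

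A later SAP cannot settle this. Section 10 requires it only before database lock, and cohort decisions are made long before that.

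**Working it through.** **Plan's own figure.** The Part A window is a 6-day run-in (one dose on day 1, then off) plus 28 days: 6 + 28 = 34 days, as stated.

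**Planned FWD1802 doses in the window.** Part A: 1 + 28 = 29. Part B: 28.

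**Fewest doses taken, with the hold placed at its worst position inside the window:**

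| Hold | Source | Part A | Part B |
|---|---|---|---|
| 14 days | Table 9, grade 2 restart limit | 29 − 14 = 15/29 (52%) | 28 − 14 = 14/28 (50%) |
| 21 days | Table 9, grade 4 restart limit | 29 − 21 = 8/29 (28%) | 28 − 21 = 7/28 (25%) |
| 28 days | 4.7.3 | 29 − 28 = 1/29 (3%) | 28 − 27 = 1/28 (4%) |

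In Part B a 28-day hold starting on day 2 covers 27 days of the window. In every row the patient reaches the end of the window, and if no 4.6 criterion is met she counts as DLT-free.

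**Effect on escalation.** Let p be the true DLT probability for a fully exposed patient. The rule escalates on 0 of 3, or on 1 of 3 followed by 0 of 3.

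- All exposed: E₀ = (1−p)³ + 3p(1−p)² × (1−p)³
- One of the first three has no DLT risk: E₁ = (1−p)² + 2p(1−p) × (1−p)³

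At p = 0.40:
- E₀ = 0.216 + 0.432 × 0.216 = 0.309
- E₁ = 0.360 + 0.480 × 0.216 = 0.464

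| Assumed p | E₀ | E₁ |
|---|---|---|
| 0.33 | 0.434 | 0.582 |
| 0.40 | 0.309 | 0.464 |
| 0.50 | 0.172 | 0.312 |

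The documents give neither p nor the frequency of holds, so p is shown over a range and no frequency is assumed: E₁ is conditional on one such patient being present. It is an upper bound, because a held patient has taken some doses and is still observed.

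**Minimum-dose threshold.** 75% of 29 is 21.75, so 22 doses in Part A. 75% of 28 is 21 doses in Part B.

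**The case against.** The strongest reply is that escalation is not automatic. The SMC decides at each level (4.2.1, 4.4) and could discount an under-dosed patient. That is a real safeguard, but no rule requires it, and the written criterion points the other way.

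Other protections are partial. At 25 mg, a grade 2 or higher event in the first patient (unless clearly due to progression or an extraneous cause) already expands the cohort to three. ALT or AST above 5 × ULN for more than two weeks is itself a DLT. Neither covers the general case.

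Three stronger readings are tempting, and the documents do not support them.

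- *4.7.1 and Table 9 contradict each other.* A reader might infer this because Table 9 orders a one-level-lower restart with no exception for the window. But the table sits under the 4.7.1 sentence that confines reductions to after the window, and that sentence can be read as its scope. The obvious example, grade 4 neutropenia too short to meet "CTCAE Grade 4 neutropenia lasting >7 days", is narrow: Table 9 stops drug only if there are symptoms, and febrile neutropenia is already a DLT. What remains is that no restart dose is given for grade 3 or 4 events inside the window.
- *Near-zero exposure is the typical case.* It needs the full 28 days of 4.7.3, while that section also refers to Table 9's shorter limits. The 25–52% range is the fair one to rely on.
- *Such holds will be common in Part B.* Table 6 shows 11% grade 4 neutropenia, but for fulvestrant plus palbociclib over the whole treatment (0% without palbociclib). No cycle 1 rate or hold rate for FWD1802 is given.

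It is also fair to say that the plan nowhere states that a held patient tolerated the dose. The count follows from the wording of 4.4 together with the absence of any evaluability rule.

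**Conclusion.** The counting fault holds and should be corrected before cohorts are assessed. As written, a patient with 25–52% of planned doses, under Table 9's own restart limits, can count as a non-DLT in the decision to escalate or to declare the MTD. The bias is towards escalation. Its size is bounded rather than known: at an assumed true DLT rate of 40%, one effectively unexposed patient among the first three raises the chance of escalating from 31% to at most 46% (from 43% to 58% at a rate of 33%; from 17% to 31% at 50%). How often this would happen cannot be derived from the documents. The relation between Table 9 and 4.7.1 is a secondary point of clarity and not a contradiction on which the finding depends.

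**What to change.** - **4.4/4.6:** Define a patient as DLT-evaluable only if she has a DLT, or receives a stated minimum of planned FWD1802 doses at the assigned level in the window. For example, at least 75%: 22 of 29 in Part A, 21 of 28 in Part B. The threshold is a choice; what matters is fixing one in advance.
- **Replacement:** Replace patients who fall below the minimum for reasons other than drug toxicity.
- **Toxicity holds:** Where a treatment-related hold takes a patient below the minimum, have the SMC decide under a pre-stated rule whether it counts as a DLT. She may not be counted as DLT-free. Making every such hold an automatic DLT would change the DLT definition and is not needed.
- **4.7.1/Table 9, for clarity:** State that the one-level-lower restarts for grades 3 and 4 apply only after the window, and that a patient who needs a reduction inside it is not counted as having tolerated the cohort dose.

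The cost is protocol wording and possibly a few replacement patients. The Part A maximum of 27 in 4.2.1 equals 3 + 4 × 6 and leaves no room for replacements if every cohort fills, so it should read 27 DLT-evaluable patients.
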